### **Four study groups will be formed.**

- Group 1: 20 persons who have received the Oxford/AstraZeneca vaccine (ChAdOx1 nCoV-19).
- Group 2: 20 persons who received the Gamaleya National Center vaccine (Sputnik V).
- Group 3: 20 people who have received the Pfizer/BioNTech vaccine (BNT162b2)
- Group 4: 20 persons who have received Sinovac vaccine (CoronaVac)

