#### **Elimination criteria:**

- 1.- Subjects who during the study develop COVID-19.
- 2.- Subjects who decide to leave the study before the stipulated time for the collection of the required blood samples.

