#### **Procedure:**

(a) Participants were selected by clinical history to assess current health status, obtain demographic data, as well as personal pathological history of importance for the study (chronic degenerative diseases, history of COVID-19 disease).

b) Peripheral venous blood samples (3 ml per occasion) will be taken from all participants. They will be carried out on days 30,60 and 120 after completion of the COVID-19 vaccination schedule.

c) Sample processing:

tRNA extraction from all samples.

cDNA synthesis

Real time PCR performance.

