### **Statistical analysis**

Descriptive phase: The results were presented in tables for continuous variables with normal distribution in measurements  $\pm$  standard deviation and for free distribution in medians and percentiles. While the categorical variables were presented in percentages and total figures.

Bivariate phase: To look for differences in the quantitative variables according to the Kolmogorov-Smirnov normality test, the student t test or the Mann-Whitney U test were used or for the related ordinal variables the Wilcoxon test. The dichotomous or ordinal related qualitative variables were analyzed with the McNemar test, for the dichotomous or ordinal variables not related they were analyzed with the chi square test or Fisher's exact test.

Multivariate phase: To compare and find the differences in more than two groups in the quantitative variables with free distribution the Kruskall-Wallis test; for the related samples with free distribution the Friedman test was used. All calculations were performed using the current version of the SPSS statistical package for Windows and the Jamovi program version 4.1 of R. Statistical significance was considered to be a P value  $<0.05$  and a confidence interval of 95%.

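### The Friedman test drops any remaining participant with one missing sample out of three; a method using every available sample would recover a modest amount of power at little cost

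*Combined protocol and SAP*

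**What the plan says.** The Procedure section (item b) plans three blood draws per participant: "They will be carried out on days 30,60 and 120 after completion of the COVID-19 vaccination schedule". "Four study groups will be formed", each of 20 people who received the same vaccine, which makes 80 participants and 240 planned samples.

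In the Statistical analysis section, the multivariate phase gives Kruskal-Wallis for comparing more than two groups and, for repeated measurements, "for the related samples with free distribution the Friedman test was used". The bivariate phase also lists a paired method, "for the related ordinal variables the Wilcoxon test", but does not offer it as a fallback for incomplete data. No method is named for three related samples that are normally distributed.

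The Elimination criteria remove two kinds of participant: "Subjects who during the study develop COVID-19" and "Subjects who decide to leave the study before the stipulated time for the collection of the required blood samples". The documents do not say what happens when someone who stays in misses a draw, or when an extraction or PCR fails. They name no imputation, incomplete-block test or mixed model, and assume no missing-sample rate.

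**The concern.** Friedman ranks the three days within each person, so a person with two values contributes nothing to it. Someone who misses one visit, or whose assay fails once, has neither decided to leave nor developed COVID-19. On its wording the elimination rule keeps that person, yet the time test leaves them out. Relaxing the elimination rule would not solve this, because the people restored would also bring incomplete triplets.

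Two things are at stake. The first is precision in the within-person comparison over time, in groups of only 20. The second is clarity: day-specific medians and Kruskal-Wallis tests could describe more people than the time test does, and nothing in the plan would show the reader the difference.

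**Working it through.** **Inputs from the documents.** Three draws per person (Procedure, item b); four groups of 20 (list of study groups); Friedman for related samples and a significance threshold of 0.05 (Statistical analysis). The plan gives no sample-size derivation, power, effect size or SD, so there is no figure of its own to reproduce.

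**Assumptions.** Each sample is lost independently with probability f = 5%, 10% or 15%. For power: log2 expression falls by 1.0 from day 30 to day 120 in equal steps, within-person SD 1.0, between-person SD 1.5, normal data, one vaccine group of 20.

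**Step 1: complete triplets per group, 20(1 − f)³.**
- f = 5%: 20 × 0.857 = 17.1
- f = 10%: 20 × 0.729 = 14.6
- f = 15%: 20 × 0.614 = 12.3

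**Step 2: share of usable samples the time test omits.** A participant has on average 3(1 − f) usable samples, of which 3(1 − f)³ sit in complete triplets. The omitted share is 1 − (1 − f)².
- f = 5%: 1 − 0.9025 = 10%, or 22.2 of 228 samples over all 80 participants
- f = 10%: 1 − 0.81 = 19%, or 41.0 of 216
- f = 15%: 1 − 0.7225 = 28%, or 56.6 of 204

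Most of these come from people with exactly one sample missing, 80 × 3f(1 − f)² = 10.8, 19.4 and 26.0 participants. Their two remaining values make 21.7, 38.9 and 52.0 samples that a method for incomplete triplets can use.

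At f = 2% only 4% of usable samples are omitted, but a group of 20 still has a 1 − 0.98⁶⁰ = 70% chance of at least one incomplete triplet.

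**Step 3: power, by simulation.** The normal-theory model is an F test with participant and day effects, standing in for the mixed model. It was run on complete triplets and on all samples, so that the effect of keeping data is separated from the effect of changing the test. Ranges show the spread between separate simulations of 1,500 to 4,000 runs per setting where results differ.

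| Samples lost (assumed) | Friedman, complete triplets | Skillings-Mack, all samples | Model, complete triplets | Model, all samples |
|---|---|---|---|---|
| 0% | 63–65% | same as Friedman | 78% | 78% |
| 5% | 56–57% | 58–59% | 70–71% | 74–75% |
| 10% | 49–50% | 52–57% | 64% | 71% |
| 15% | 42–43% | 49–51% | 56% | 66% |

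Type I error was about 4–6% for all methods. Keeping incomplete triplets gains about 1 to 8 points with Skillings-Mack and about 5 to 10 points within the model (4 to 11 across individual simulations).

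If the same fraction of triplets is broken but every loss is at day 120, the gains shrink to about 1 to 5 points for Skillings-Mack and 2 to 8 for the model, because the retained pairs then inform only day 30 against day 60.

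A second setting (decline of 0.8 within-person SD, 2,000 runs) gives Friedman against Skillings-Mack 46% and 46% with no loss, 38% and 40% at 5%, 33% and 36% at 10%, and 25% and 31% at 20%.

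**The case against.** **The power gap is mostly not about missing data.** A reader might set Friedman's 56% beside the model's 75% at 5% loss and blame the 19 points on dropped triplets. That is wrong. With nothing missing the gap is already about 14 points (64% against 78%), because a rank test is being compared with a normal-theory test on simulated normal data. This part of the objection stands in full.

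**The lost values are not wasted.** The plan does not tie Friedman to the three days in so many words, and the remaining values can enter Kruskal-Wallis tests by day or a pairwise Wilcoxon test. This stands too. The omission concerns only the three-day comparison, although the three draws are the only repeated measurements described and no other test for more than two related samples is named.

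**The investigators may treat all three samples as required.** The elimination rule does refer to required samples, and if only completers were analysed, all results would share one subset. But the rule is worded around a decision to leave and is silent on a missed visit or failed assay. At the least, the handling is unstated.

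**A mixed model conflicts with the plan's own condition.** Friedman is reserved for non-normal data, and nothing in the documents shows that log expression is normal. This stands against making the mixed model the sole replacement. It does not touch Skillings-Mack, which needs no normality.

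**No bias is shown.** Correct. The simulations delete samples at random and can show only lost precision.

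**Conclusion.** The point holds as a modest loss of precision that is cheap to avoid. Friedman remains a valid test, with type I error near its nominal level. The omitted share, 10% to 28% of usable samples at 5% to 15% independent loss, follows directly from needing three values per person. The power recovered is much smaller: about 1 to 8 points with Skillings-Mack or 5 to 10 within a normal-theory model, and less when losses are concentrated at day 120.

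All of this rests on assumed loss rates, effect size and SDs, and on reading Friedman as the test for the three draws. At 2% loss the effect would be small. Losses at day 120 are plausible if draws are prospective: the Schedule ends collection in December 2021, and day 120 is 90 days after day 30, so a day-30 draw after about 2 October would put day 120 beyond that window. The Methodology section also calls the study retrospective, so this is conditional.

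A reader might also infer that the time result would be biased because it rests on a selected subset. The documents give no reason why samples would be missing, so that inference is not supported.

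**What to change.** Revise the multivariate phase of the Statistical analysis section as follows:

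- Where data are non-normal, replace Friedman with Skillings-Mack, using every available sample. The two tests are identical when all triplets are complete, so nothing changes if no sample is lost.
- Where log expression is roughly normal, use a linear mixed model with day as a factor and participant as a random effect. This also fills the gap left by the absence of any method for three related normal samples.
- Keep Friedman on complete triplets as a sensitivity analysis.
- Report the number of samples by day and vaccine, so that readers can see who contributes to each result.

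The cost is new wording and a little more analysis work; no extra blood draws are needed. Mixed models run in SPSS and R, and the team should confirm how it will run Skillings-Mack in its chosen software. The downside lies in the assumptions: Skillings-Mack takes samples to be missing completely at random, and the mixed model takes them to be missing at random with approximately normal log expression.
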